2. OBJECTIVES

The primary objectives of this study are:

- A. To investigate if in adult patients with PTSD and comorbid PD it is more effective to provide integrated PTSD-PD treatment compared to PTSD treatment alone in terms of response rate in PTSD symptoms:
 - A1. In patients with PTSD with BPD, integrated DBT-EMDR treatment results in a higher effect size and higher response rate than EMDR-only.

A2. In patients with PTSD and CPD, integrated SFT- ImRs treatment results in a higher effect size and higher response rate than ImRs -only.

B. To investigate individually prediction by a machine-learning model of PTSD treatment outcome in adult patients with comorbid PTSD and personality disorders (profiling), in order to improve treatment indication leading to more precise (personalized) and efficient treatments, with candidate predictors:

B1. Psychological factors: cognitive (educational level/IQ, working memory, emotion regulation), affective (hyper-arousal: anger, sleep; hyper-arousal: dissociation), and relational factors (therapeutic alliance, attachment, social support).

B2. Neurobiological factors: Neural factors (smaller ACC and hippocampus volume, increased right amygdala and ventral ACC activity and de/increased dorsal ACC activity), and Hormonal/ epigenetic factors (5-HTTLPR, BDNF, cortisol/FKBP5-methylation, oxytocin/OXTR).

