to be associated with worse outcome of PTSD treatment. These are cognitive (educational level, working memory emotion regulation), affective (anger, sleep problems, dissociation), and relational factors (therapeutic alliance, attachment, social support). In addition, neurobiological factors are found to be associated with PTSD treatment outcome, such as increased activity connectivity of the limbic network and decreased activity and connectivity of the cognitive control networks, and disturbed hormonal levels and epigenetic factors (5-HTTLPR, BDNF, cortisol/FKBP5-methylation, oxytocin/OXTR). Because these candidate predictors are found on a group level (in non-responders vs. responders), they cannot directly be used on an individual level. By using machine-learning techniques we might use these candidate predictors on an individual level to guide treatment choices and thereby personalise psychiatry.

We hypothesize that in patients with PTSD with BPD, integrated DBT-EMDR treatment results in a higher effect size and higher response rate than EMDR-only (A1); in patients with PTSD and CPD, integrated SFT- ImRs treatment results in a higher effect size and higher response rate than ImRs only (A2). Furthermore, we hypothesize that non-response to PTSD-treatment can be individually predicted by a machine-learning model with (B1) psychological factors (cognitive, affective, and relational) and (B2) neurobiological factors (neural factors, and hormonal/ epigenetic factors).

Objective: In the current project, we will firstly study effectiveness of PTSD-treatment compared to integrated PTSD-PD-treatment in treatment-seeking, adult patients with comorbid PTSD and PD in a wide range of severity (minimally 4 criteria of a personality disorder). Secondly, we will investigate psychological (cognitive, affective, and relational) and neurobiological candidate predictors of treatment outcome, and use them in a machine-learning paradigm to come to a clinically useful and individual prediction instrument of treatment outcome.

Study design: Two related randomized controlled trials (A1, A2) with prediction analyses (B1, B2).

Study population: With the assumptions of a small effect size (< 0.5) of PTSD treatment in patients with comorbid PTSD and PD and a double effect size of integrated PTSD-PD-

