treatment (1.0), the number of persons needed to include is 50 persons per condition to reach for 80% power. Expecting a dropout rate of 25%, we will include 63 persons per arm, for 4 arms a total of 252 adult patients with PTSD and - at least 4 - PD symptoms. Of these patients, 80 next to 40 healthy matched controls will be asked for additional MRI research before and after treatment. In total, 292 persons will be included in this study.

Intervention: In patients with PTSD and BPD: EMDR (3-6 months plus 6-9 months treatment pause) compared to integrated DBT-EMDR (12 months); in patients with PTSD and CPD: ImRs (3-6 months plus 6-9 months treatment pause) compared to integrated ImRs-SFT (12 months).

Main study parameters/endpoints: Primary outcome measure is PTSD symptom severity after 12 months. Secondary outcome measures are PD symptoms (SCID-5-PD), disability (WHODAS), quality of life (EQ-5D-5L) and health costs (Tic-P). At baseline (T₀) and after 12 months (T₄) clinical interviews (CAPS-5, SCID-5-PD dimensional score) and self-rating scales (PCL-5) will be used. After 3 (T₁), 6 (T₂), 9 (T₃), and 18 months (follow-up), questionnaires only will be used. At baseline, candidate predictors will be measured including above mentioned cognitive, affective, relational factors, and hormonal and epigenetic factors. In a subgroup, structural and functional MRI, with resting-state and an emotion processing (face recognition) will be performed.

Nature and extent of the burden and risks associated with participation and benefits:

The burden and risks associated with participation in this study is reasonable. All patients will receive psychotherapy, which is considered to be the most effective treatment for PTSD and PD. There is evidence that all four conditions are therapeutic in patients with PTSD and PD and no evidence yet what condition is more effective. Total time of the six measurements is approximately 5 hours per patient for interviews and 5 hours for questionnaires (see table 3), which are partly part of the routine outcome measurements (ROM). Questionnaires can be filled in at home. On the one hand, extensive clinical interviews and self-rating scales can be felt as disturbing because of fatigue, taken time and emotional burden. On the other hand, patients may feel well recognized by the time taken by specialized clinicians for them. Assessors will be well-trained and work in close

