For PTSD with comorbid (B)PD an integrated DBT-PTSD-treatment is investigated in 3 RCTs (Steil et al., 2011, Bohus et al., 2013, Harned et al., 2014). The first study showed moderate to large effect sizes of DBT-PTSD compared to waiting list, in terms of overall BPD severity (SMD -0.74 [95%CI -1.47 - -0.01]), depression (SMD -1.06 [95% CI -1.84 - -0.29]), and anxiety (SMD -0.96 [95% CI -1.72 - -0.20]) (Steil et al., 2011). The second study indicated that DBT-PTSD resulted in a greater mean change than waiting list on PTSD symptoms (CAPS 33.16 vs. 2.08), but not on BPD symptoms (Bohus et al., 2013). Integrated DBT-PTSD-treatment was also compared to DBT-alone, and led to larger and more stable improvements in PTSD symptoms, doubled remission rate (80% vs. 40%), and decreased suicide rates (2.4 times less likely) and self-injury (1.5 times less likely), with moderate to large effect sizes for dissociation, trauma-related guilt cognitions, shame, anxiety, depression, and global functioning in completers (Harned et al., 2014). However, integrated PTSD-PD treatment is not yet directly compared to PTSD treatment alone.

In summary, there is growing motivation in clinicians to offer PTSD treatments to PTSD with comorbid disorders, because these treatments are highly effective, relatively short, and there is some evidence that with PTSD treatment, comorbid PD symptoms might resolve as well. However, it may be more efficient to add a PD treatment at the same time. Evidence-based treatments for personality disorders (PD), such as dialectical behaviour treatment (DBT) for BPD, and schema-focused treatment (SFT) for CPD are well established. These treatments are more intensive (twice a week for at least one year) than PTSD treatments. There is some evidence that integrated PTSD-PD treatment works twice as good as PD treatment alone, but integrated PTSDPD treatment is not yet directly compared to PTSD treatment alone. This study will address this knowledge gap.

Hypotheses A: We hypothesize that in PTSD with comorbid PD it is more effective to provide integrated PTSD-PD-treatment compared to PTSD treatment alone, primarily in terms of response rate in PTSD symptoms. Secondly, we hypothesize that PD symptoms, disability and quality of life will improve and cost-effectiveness will be better with integrated treatment.

- A1. In patients with PTSD with BPD, integrated DBT-EMDR treatment results in a higher response rate than EMDR-only;

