4.4 Sample size calculation

A power calculation was made based on Twisk (2007). We assume that PTSD treatment (EMDR or ImRs) have a small effect size (< 0.5) in the complex patient group with PTSD and comorbid

CPD/BPD, while the integrated treatment will show double effect sizes (1.0) (Harned et al., 2014). With a minimal clinical relevant difference of a 0.5SD on the CAPS-5, and the assumptions of a SD of 20.0, an intra-person correlation coefficient of 0.7, 5 follow-up measurements, the needed number to include is 50 persons per condition to reach for 80% power. Expecting a drop-out rate of 25%, we will include 63 persons per arm, or for 4 arms in total 252 persons.

In 2016, approximately 950 new patients were referred to the SC (Amstelveen). From these patients, ca. 450 had PTSD. From these PTSD patients, 168 had a comorbid PD and 188 more were not assessed for personality traits (“Uitgestelde diagnose”). We expect that introducing the assessment of axis II assessments with this study will result in an estimated 300 patients with PTSD and PD per year, and after 33% refusals or exclusions, in an estimated 200 patients possible to include per year. To be sure to include enough patients, we will need to include more patients from another site of the

Sinai Center, i.e. Amersfoort (400 patients, from which 216 PTSD patients, from which an estimated 100 PTSD + PD patients), and extend the inclusion period.

From these 252 patients, 80 will be asked for additional MRI, next to 40 healthy controls (Total sample size = 292). An estimated 40 patients will be available for a second MRI after 6 months (total of 160 scan sessions).

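### Objective A is framed as response rate while the outcome, sample size and primary model use CAPS-5 severity; response has no between-arm test, and Section 7.1 names no deciding contrast and uses T0 as both outcome and covariate

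*Combined protocol and SAP*

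**What the plan says.** **Response framing.** Hypotheses A in Section 1 pose the question "primarily in terms of response rate in PTSD symptoms". The stem of Objective A in Section 2 asks whether "it is more effective to provide integrated PTSD-PD treatment compared to PTSD treatment alone in terms of response rate in PTSD symptoms". Sub-objective A1 then says that the integrated treatment "results in a higher effect size and higher response rate than EMDR-only"; A2 is worded the same way, and neither ranks the two measures.

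**Severity framing.** The Summary states: "Primary outcome measure is PTSD symptom severity after 12 months". Section 5.1.1 lists only the summed CAPS-5 severity score. Section 4.4 sizes the trial "With a minimal clinical relevant difference of a 0.5SD on the CAPS-5", with an SD of 20.0, "an intra-person correlation coefficient of 0.7, 5 follow-up measurements", giving 50 per condition for 80% power and 63 per arm after 25% dropout.

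**Analysis.** The primary analysis in Section 7.1 is a linear mixed model of CAPS-5 at T0, T2 and T4, with time, arm, their interaction, the baseline score as covariate, a random intercept and an autoregressive residual structure. One sentence defines a responder as someone who ends at least 1 SD below the starting score, citing a methods paper on clinically meaningful change. The only stated analysis of responder status is the machine-learning classification. Response is in neither 5.1.1 nor 5.1.2, and 7.2 and 7.3 add no test of it.

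**Visits.** Table 1 schedules CAPS-5 at T0, T2 and T4. For the 3-, 6-, 9- and 18-month visits the Summary says that at "18 months (follow-up), questionnaires only will be used", which conflicts with CAPS-5 at T2 in Table 1, 5.3 and 7.1. The research questions in 5.3 ask about 12 months for A1 but 6, 12 and 18 months for A2.

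**The concern.** Four gaps meet at the primary claim.

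- The measure named in the stem of the objective is not the one that is sized or modelled. Its response half has a definition but no between-arm test, no visit for the final score and no statement of which SD applies.
- Section 7.1 does not say whether T2, T4 or the overall interaction decides, so more than one result could be presented as primary.
- T0 appears on both sides of the model. An analyst who takes the natural 12-month contrast from it would use a standard error that is too small.
- A reader may take the 80% power to cover response or the 12-month comparison. It was derived for neither, and it counts more CAPS-5 visits than are scheduled.

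**Working it through.** **Inputs.** Section 4.4 gives a difference of 0.5 SD (10 points at SD 20), correlation 0.7, 5 follow-ups, 50 per arm, and 63 per arm with 25% dropout; 63 × 0.75 = 47 evaluable. Section 4.4 states neither alpha nor sidedness, so two-sided 5% is assumed.

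**1. The plan's own figure.** For a difference averaged over T follow-ups, n per arm = 2(1.960 + 0.842)² × f / 0.5², where f = [1 + (T − 1) × 0.7] / T.

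- T = 5: f = 0.76, n = 47.7, so 48, close to the stated 50. The 80% is therefore for mean severity averaged over five follow-ups.
- T = 2 (the CAPS-5 follow-ups in Table 1): f = 0.85, n = 53.4, so 54. Power (t test) is about 77% at 50 evaluable per arm and about 74% at 47.

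**2. A single T4 contrast.** Here f = 1 without baseline adjustment and f = 1 − r² with T0 as covariate, r being the T0–T4 correlation. Power at 47 evaluable per arm (t test):

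- unadjusted, f = 1: 67%
- r = 0.4, f = 0.84: 74%
- r = 0.5, f = 0.75: 79%
- r = 0.7, f = 0.51: 92%

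**3. T0 as outcome and covariate.** Set the SD to 1 and all pairwise correlations to 0.7, with 50 per arm, complete data and no treatment effect.

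- The model has one slope for the baseline score across all three visits. It estimates the average of the visit-specific slopes, (1 + 0.7 + 0.7)/3 = 0.8.
- Residual variance is (1 − 0.8)² = 0.04 at T0, and 1 + 0.64 − 2 × 0.8 × 0.7 = 0.52 at T2 and at T4.
- A random-intercept model assumes one common variance: (0.04 + 0.52 + 0.52)/3 = 0.36.
- Its standard error for the T4 difference is √(2 × 0.36/50) = 0.12. The true value is √(2 × 0.52/50) = 0.144.
- The chance of a false positive is 2[1 − Φ(1.96 × 0.12/0.144)] = 2[1 − Φ(1.63)], about 10%.

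Simulation of this model agrees: about 11% rejections against a nominal 5%. Separate runs gave 12% (800 trials) and, with an AR(1) residual term added, 9% (only 300 trials).

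The change-from-T0 interaction is not affected in this way. The residual covariances are 0.2 × (0.7 − 0.8) = −0.02 for T0 with T2 and with T4, and 0.7 − 2 × 0.8 × 0.7 + 0.64 = 0.22 for T2 with T4; their mean is 0.06. The model's within-subject variance is then 0.36 − 0.06 = 0.30, so the variance of the interaction is 4 × 0.30/50 = 0.024. The true variance is 2 × [2(1 − 0.7)]/50 = 0.024. In simulation it rejected 3% to 7% of the time.

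**The case against.** The strongest reply is that the intended endpoint is plain. The Summary states 12-month severity outright, 4.4, 5.1.1 and 7.1 all use severity, and A1 and A2 name effect size, which the mixed model addresses. That stands. A reader might infer that the plan does not test its primary objective at all; the documents do not support this, because only the response half lacks a test. Nor is the 12-month visit missing from the plan. It is missing from 7.1, and the A2 question in 5.3 departs from it.

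It can also be said that a baseline-adjusted difference and a difference in change from T0 estimate the same quantity under randomisation. That is right, so the choice between them is not an ambiguity of endpoint. They differ in precision, and in the model as written only the change contrast keeps its error rate.

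The responder rule does cite a source for its 1 SD threshold; what it lacks is which SD and which visit. The 18-month A2 question does not name the CAPS-5, and the PCL-5 is scheduled then, so it can be answered from questionnaires.

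Finally, any power figure for response must be built on assumed response rates, because the documents give none for these comparisons. With improvements of 0.5 versus 1.0 SD and normal scores, a simple comparison at 50 per arm has power of 38% at r = 0.3, 50% at r = 0.5 and 70% at r = 0.7. That spread is too wide to put a figure in the protocol. The sponsor could instead keep response as primary, but would then have to specify and size a test for it.

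**Conclusion.** The point holds. The primary question is framed as response in Hypotheses A and the stem of Objective A, and as continuous severity wherever the trial is sized and analysed. Response has no between-arm test, and 7.1 names no deciding visit or contrast. These findings rest on the text alone.

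Two sizes depend on assumptions. The T4 contrast from the model as written has a type I error of about 11% (random intercept, 50 per arm, equal correlations of 0.7, complete data). The stated 80% becomes about 77% at 50 evaluable per arm, or 74% at 47, for the average over the two actual CAPS-5 follow-ups (two-sided 5% alpha).

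A reader might infer that the trial is too small for 12-month severity, or equally that 63 per arm is clearly enough. Neither follows. At 47 evaluable per arm, a properly specified baseline-adjusted contrast has 92% power at r = 0.7 but 79% at r = 0.5. The single 0.7 in 4.4 is not said to hold between T0 and T4, twelve months apart. This should be fixed, and it can be done in wording.

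**What to change.** 1. Align the Summary hypotheses, Hypotheses A, Section 2 and the 5.3 questions with 5.1.1: CAPS-5 severity at 12 months is primary, as the Summary already says, and response is secondary.
2. In 7.1, name one primary contrast for each RCT: the between-arm difference in CAPS-5 at T4, from a mixed model with only T2 and T4 as outcomes and T0 entered once, as covariate.
3. Define response at T4 with one prespecified SD and a between-arm test, for example logistic regression adjusted for baseline CAPS-5.
4. Restate power in 4.4 for that contrast, using the actual CAPS-5 visits and showing the T0–T4 correlation assumption: at 47 evaluable per arm, about 92% at r = 0.7, 79% at 0.5, 74% at 0.4, and 67% unadjusted. State alpha and sidedness. Say that the 80% was not derived for response, and give no response power figure.
5. Correct the Summary on CAPS-5 at T2, and state that 18-month comparisons rest on questionnaires such as the PCL-5.

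The cost is protocol wording, a power statement that is conditional and may be less favourable, and the loss of primary status for response. Patient numbers and visits do not change.

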3. STUDY DESIGN

The design of this study consists of two – connected - RCTs comparing PTSD-treatment to integrated PTSD-PD treatment in patients with PTSD and comorbid PD in a specialized treatment setting (figure 2):

A1. EMDR versus integrated DBT-EMDR, and

A2. ImRs versus integrated SFT- ImRs.

Assessment points are: baseline (T₀), after 3 months (T₁), after trauma treatment has finished, around 6 months (T₂), 3 months after T₂ (T₃), after 12 months (T₄) and at 18 months (follow-up, FU).

PTSD treatments specifically address the troubling memories of the traumatic event and the personal meaning of the event and consist of 12 to 18 sessions in maximum 6 months, and are:

- EMDR (Eye Movement Desensitization and Reprocessing)

EMDR was developed in 1987 by Shapiro (De Jongh & Ten Broeke, 1998). In EMDR the therapist induces a bilateral stimulation once the client has focused the attention on a disturbing image or memory related to the traumatic experience. The bilateral stimulation is induced by the movement of the therapist's fingers in front of the patients face from

the left to the right with the instruction for the client to follow this movement of the hand with the eyes. Attention is drawn to what traumatic memory and the dysfunctional thoughts about it are currently doing with the patient and not to what the patient was thinking during the traumatic experience.

- ImRs (Imagination and Rescripting Therapy) (Arntz et al., 2007, Raabe et al., 2015).

In ImRs, the patient imagines the (onset of a) traumatic experience and subsequently changes the original course of events by imagining different interventions and outcomes, thereby allowing for the change of original schematic representations and cognitions (Hackmann et al., 2011). ImRs implies changing the traumatic imagery in fantasy, to produce a more favourable outcome (without denying the trauma), imagining having control over the situation and being able to act according to one's needs, to express one's feelings and action tendencies. ImRs was hypothesized to alleviate PTSD symptoms as well as change trauma-related beliefs and schemas (e.g. powerlessness, victimization, and inherent badness). It is suggested that ImRs might be more effective in patients with emotions and cognitions like anger, irrational guilt, shame disgust and/or self-contempt (Arntz et al., 2007).

Integrated PTSD-PD treatment consist of a PTSD treatment interwoven in a PD treatment that takes at least twice sessions per week, for the duration of one year:

- DBT (Dialectical Behavior Treatment), a manualized outpatient cognitive-behavioral treatment with two components: (a) weekly individual therapy and (b) weekly group skills training. Individual sessions focus on a hierarchy of target behaviors, which the patient tracks on a daily basis with diary cards. Behavioral analyses of the pattern and chain of thoughts, emotions, and events take place routinely to help the patient identify triggers and alternative strategies for coping. Change strategies such as problem solving and reinforcement techniques are used in combination with acceptance and validation of the patient's experience. Group skills' training is used to help patients develop less self-destructive and more adaptive means of coping with intolerable affects. These skills include awareness of emotions and reactions, interpersonal effectiveness, emotion regulation, and distress tolerance. Skills are then integrated into the individual treatment in problem situations, e.g. suicidal urges (Linehan, 1993).

- SFT (schema focused treatment) is a form of psychotherapy integrating cognitive therapy, behavior therapy, object relations, and gestalt therapy into one unified,

systematic approach to treatment. The focus in SFT is on changing maladaptive schemes that patients develop early in life and thereby improve emotion regulation skills. Change is achieved through a range of behavioral, cognitive, and experiential techniques that focus on (1) the therapeutic relationship, (2) daily life outside therapy (also through homework assignments), and (3) past (traumatic) experiences (Young et al., 2003). Psychomotor therapy (PMT) is part of the SFT treatment protocol.

[figure not shown]
In the Sinai Centrum, 2 “Zorgpaden” will be implemented in Fall2017:

“Zorgpad 1” with EMDR or ImRs (3-6 months) and Zorgpad 2” with EMDR-DBT or ImRs - SFT (9-12 months). Therapists need to be “adherent-to-the model”, which will be ascertained by regular supervision with audiovisual recordings based on the different theoretical psychotherapeutic principles and therapies are delivered by protocol. At this moment, there is no clear scientific evidence and criteria are not explicitly defined for the one or the other treatment, except that patients with PTSD without comorbid PD have to be indicated for “Zorgpad” 1.

Use of co-intervention: Patients may continue taking medication for PTSD throughout the study. Patients who started with new medication for PTSD within 1 month prior to the initial screening will be excluded from participation. No other psychological or new pharmacological therapy is allowed during treatment. Medication use is monitored during the study.

Escape medication/treatment: Participants might start taking medication or another form of treatment/therapy in case of acute crisis during the study. The use of these medications or crisis intervention during the study as co-intervention will not lead to exclusion from the study, but will be monitored, documented, and reported.

Further treatment: After completion of the EMDR or ImRs a first follow-up assessment will be completed and the therapist will see the patient for an evaluation. If more treatment is acutely needed, a clinical evaluation is done and the indication staff will decide what treatment to offer to the patient. The kind, intensity and frequency of this further treatment will be monitored, documented and reported. All patients in Zorgpad 1 are allowed to start SFT or DBT after T4 (i.e. 6 months after completing Zorgpad 1).

18

Figure 2. Flow chart for two connected randomized controlled trials (RCTs) for patients with PTSD and borderline personality disorders (BPD) resp. with PTSD and cluster C personality disorders (CPD)

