7.1 Primary study parameters

For population description, the CAPS-5, M.I.N.I.-plus, SCID-5-PD, will be used in addition to the CTQ, LEC-5, DERS, ITQ, PAI-BOR, STAS, PSQI, DES-II, WAV, RSQ, CPI, BDI, AUDIT, WHODAS, EQ5D-5L, and Tic-P will be used (see Table 1). The subgroup of patients that underwent MRI will be compared to the rest of the group to test for pretreatment differences in PTSD severity and type/severity of PD.

The primary analysis in the RCTs will be improvement of PTSD symptoms at 3 time points. This primary analysis will include trauma symptom scores at T₀, T₂ and T₄ (CAPS-5, severity score) in a repeated measurements model, a linear mixed model for repeated measurements including at least time points, treatment group, the interaction between time point and treatment, sex, age and severity as fixed factors, baseline score as covariate and subject as random intercept factor. An cAR(1) structure will be used to model the residual covariance matrix. Responders will be defined as participants with a posttest score at least 1 SD below the pretest score (based on Jacobsen and Truax, 1991).

Secondary analyses will examine whether hormonal and epigenetic factors (5-HTTLPR, BDNF, cortisol/FKBP5-methylation, oxytocin/OXTR) mediate the treatment effects. Mediation analyses will include levels of the aforementioned variables on T₀ and T₂ to estimate the direct and indirect paths of casual treatment on the primary and secondary study parameters, through the proposed mediators.

For individual prediction analyses, machine learning techniques (in R: supervised and unsupervised techniques, e.g. the random forest model method) will be applied to separate treatment responders from non-responders based on clinical and neurobiological candidate predictors and in order to define the predictors

contributing most to classification accuracy, calculating sensitivity, specificity, and positive and negative likelihood ratios from the prediction model (Ball et al., 2014).

Candidate predictors that will be used are:

- Psychological factors: Cognitive factors (educational level/IQ, working memory, emotion regulation), Affective factors (hyperarousal: anger, sleep; hyperarousal: dissociation), and Relational factors (therapeutic alliance, attachment, social support);

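### RCT A1: skills groups in the DBT-EMDR arm are not in the primary model, so the standard error is too small if CAPS-5 outcomes correlate within groups

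*Combined protocol and SAP*

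**What the plan says.** Section 3 describes DBT, within an integrated treatment lasting a year, as "a) weekly individual therapy and (b) weekly group skills training". The same section describes EMDR as work between one therapist and one patient and mentions no group. Under section 5.2.1 patients are randomised individually, in blocks of four per site.

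The primary analysis in section 7.1 is a linear mixed model of CAPS-5 severity at T0, T2 and T4. It has fixed factors, a baseline covariate, "subject as random intercept factor", and an autoregressive residual structure. Sections 7.2 and 7.3 carry a similar model over to the secondary and other outcomes.

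Section 4.4 states that "the needed number to include is 50 persons per condition to reach for 80% power". The only correlation it uses is within a person: "an intra-person correlation coefficient of 0.7, 5 follow-up measurements". The documents give no skills-group size, number of groups, between-patient correlation or therapist effect, and they do not say that group membership will be recorded.

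**The concern.** Skills groups form after randomisation and in one arm of A1 only, which makes this a partially nested design. Patients in the same group share peers and trainers for months, and both post-baseline CAPS-5 assessments fall during or at the end of that period. Their outcomes may therefore be correlated.

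The subject intercept and the autoregressive residuals link a patient's own time points and never link two patients. Baseline adjustment cannot remove a correlation that arises after randomisation.

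If the correlation is positive, the model understates the variance of the DBT-EMDR mean. The A1 confidence interval is then too narrow and the nominal 5% test has a higher true error rate. The power claimed in section 4.4 would also be optimistic.

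**Working it through.** **1. The plan's own figure.** Inputs from section 4.4: "a minimal clinical relevant difference of a 0.5SD on the CAPS-5" with "the assumptions of a SD of 20.0", so δ = 10 points; within-person correlation ρ = 0.7; T = 5 measurements; power 80%. Alpha is not stated; 0.05 two-sided is assumed. The standard repeated-measures formula, also an assumption, is

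n per arm = 2(z₁₋α/₂ + z₁₋β)² · SD² · [1 + (T−1)ρ] / (T·δ²)

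= 2 × (1.960 + 0.842)² × 400 × 3.8 / (5 × 100) = 47.7, so 48.

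This is within two patients of the stated 50. One-sided 0.05 would give 38. The stated number is thus recovered by a calculation with no allowance for between-patient correlation.

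**2. Effect of clustering in one arm.** Let m be the number of analysed DBT-EMDR patients per skills group, in closed groups of equal size.

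- Design effect in the DBT-EMDR arm: DE = 1 + (m−1)·ICC; in the EMDR arm it is 1.
- True SE divided by model SE: r = √((1+DE)/2).
- Amount by which the model SE is too small: 1 − 1/r.
- True type I error of the planned test: 2[1 − Φ(1.96/r)].
- Power of the planned, unadjusted test from a nominal 80%: Φ(0.842/r).
- Power of a test using the correct SE: Φ(2.802/r − 1.96).

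The last two lines describe different tests and should not be merged.

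**3. Results.** Every m and ICC below is an assumption.

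| m | ICC | DE | r | SE too small by | Type I error | Power, planned test | Power, correct SE |
|---|---|---|---|---|---|---|---|
| 3 | 0.02 | 1.04 | 1.010 | 1.0% | 5.2% | 80% | 79% |
| 4 | 0.05 | 1.15 | 1.037 | 3.6% | 5.9% | 79% | 77% |
| 6 | 0.01 | 1.05 | 1.012 | 1.2% | 5.3% | 80% | 79% |
| 10 | 0.01 | 1.09 | 1.022 | 2.2% | 5.5% | 79% | 78% |
| 6 | 0.02 | 1.10 | 1.025 | 2.4% | 5.6% | 79% | 78% |
| 8 | 0.05 | 1.35 | 1.084 | 7.7% | 7.1% | 78% | 73% |
| 10 | 0.10 | 1.90 | 1.204 | 17.0% | 10.4% | 76% | 64% |

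On the CAPS-5 scale, with 50 analysed per arm and s² = 400 × 3.8/5 = 304, the SE ignoring groups is √(304 × 2/50) = 3.49 points. At m 8 and ICC 0.05 it is √(304 × 2.35/50) = 3.78 points.

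**4. Simulation check.** An unadjusted t-test was simulated 40,000 times with 48 per arm and closed groups. It rejected a true null in 4.9% of runs at ICC 0. At ICC 0.05 and 0.10 it rejected in 6.3% and 8.0% of runs for m = 6, and in 7.0% and 9.4% for m = 8. This agrees with the formula.

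**The case against.** **The harm is conditional.** With no ICC or group size in the documents, no distortion has been shown. At ICC 0.01 the effect is negligible. This stands.

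**The ICC on this outcome may be low.** CAPS-5 measures PTSD severity. Section 3 assigns the trauma memories to EMDR, given individually, and the skills group to coping and emotion regulation, alongside weekly individual sessions. This makes a small ICC plausible but does not prove one.

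**The number that matters is analysed trial patients per group, not group size.** Section 4.4 expects 25% dropout, so a group of 8 would hold about 6 completers. Nothing says the groups are reserved for trial patients. EMDR-only patients may start DBT after T4 and could fill places without counting in the DBT-EMDR arm. Rolling entry, on which the documents are silent, would make the closed-group formula approximate. This is why the table includes m of 3–4. None of it makes patients independent.

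**The model wording is open-ended.** Section 7.1 lists a minimum set of terms. That list concerns fixed factors, and no group effect is named. A group term added after the data are seen would not be prespecified, and it could not be fitted if membership had not been recorded.

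**Therapists may matter in both arms.** Patients who share a therapist could also be correlated, in which case treating each EMDR-only patient as independent is itself a simplification. This is fair, and the fix should address it.

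**A stronger reading is tempting.** A reader might infer that the A1 test does over-reject, at around 10%, and that its power falls to 64%. The documents do not support this. The 10.4% needs m 10 and ICC 0.10, neither of which they establish. The 64% is the power of a corrected test in that same case; the planned unadjusted test keeps about 76% there.

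**Conclusion.** The omission is real. One arm of A1 receives group-delivered treatment, and neither the primary model nor the sample size allows for it. Any positive within-group correlation makes the A1 standard error too small and the test too liberal.

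The size is unknown. On the assumed values it runs from negligible (type I error 5.2–5.5% with few analysed patients per group or a very small ICC) through moderate (7.1% at m 8, ICC 0.05) to serious (10.4% at m 10, ICC 0.10). The upper end should not be cited as what the plan will produce. For m 6–10 and ICC 0.02–0.10, power is about 76–79% for the planned test and 64–78% for a test with the correct SE, both from a nominal 80%.

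The conclusion rests on closed, equal groups, a two-sided 5% test and normal critical values. It is limited to A1. A reader might extend it to A2, but section 3 does not say that SFT is given in groups.

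**What to change.** - Record a skills-group identifier (where one applies) and a therapist identifier for every patient.
- Prespecify for A1, in section 7.1, a partially nested model: a random skills-group effect in the DBT-EMDR arm only, each EMDR-only patient as a singleton, and small-sample degrees of freedom. Report it alongside the unclustered model.
- Add a sensitivity analysis with a therapist random effect in both arms, so that the therapist identifiers are used.
- State in section 4.4 that the 80% power assumes no clustering by group.
- Apply the same to A2 only if SFT is given in groups.

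The cost is two database fields, a prespecified model term and one sensitivity analysis. The downside is a somewhat wider A1 interval and an imprecise group variance if there are few groups. For example, 63 enrolled patients in groups of 8 would make about 8 groups (63/8 = 7.9), which is why both models should be shown.
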